# Data Analysis, Statistical Considerations, and Testing of Hypotheses:

Determination of Sample Size: Hypothesis 1 concerns within-treatment group improvement of

Version #: 17, IRB #203076

PI: [name]

depression. With four post-baseline measures, calculation of power requires an estimate of the matrix of correlations among the repeated measures. We specified a medium effect size averaged across the postbaseline measures (Cohen's d=0.5 SD, 1988), unadjusted alpha of 0.05. We specified compound symmetry among the measures with r=0.50 because the measurements are relatively close in time. With these specifications, it is possible to calculate the standard error of the difference between baseline and the average of the post-baseline measures. With N=20, IBM SamplePower3's (IBM SPSS, 2000) module for the t-test for paired observations indicates power=0.78 with N=20. We confirmed this result with a simulation with 1000 datasets with the structure described, performing mixed effects analyses as described below. The simulation yielded an empirical power estimate of 0.79 for Hypothesis 1. We also evaluated a banded covariance structure in which the correlations fell off from .50 to .32 over time, and found that yielded power=0.75. Hypothesis 2 concerns between group differences. Power was calculated using Hedeker's RMASS2 software for mixed models with longitudinal data. Specifications were as above but the effect size was adjusted for the use of a baseline covariate and the design involves two groups of N=20 each assessed at four occasions. In this case, power is 0.80 to detect a standardized mean difference (Cohen's d) of 0.6. This is slightly larger than the conventional medium effect size of d=0.50. The analyses for Hypothesis 3 involves using the TRP/LNAA ratio as a covariate in mixed effects regression models with the same design structure and analytic plan as the between-groups models for Hypothesis 2. Converting Cohen's d to the correlation coefficient equivalent, d=.6 is roughly equal to r=.30. Cohen's convention for a medium correlation. Evidence that these assumptions about effect sizes are probably quite conservative can be found in previously described effects of bupropion [68, 70, 90, 116-120] and fluoxetine [28, 60, 104, 116, 121] on symptoms of major depression, cognition, and inflammation.

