General Methods: Given that a primary goal of the current study is to obtain data to justify and support the feasibility of a future definitive trial, a variety of data necessary for this, including data on tolerability and safety (see below), will be obtained. For example, subject disposition will be summarized with a table indicating the number of subjects screened, the number of screen failures by reason, the number enrolled, the number who dropped out (by reason), and the number completing the study. Random double-blind assignment of patients to fluoxetine or bupropion is expected to yield similar distributions of measured and unmeasured variables of interest. This design provides a strong basis for making inferences about causal relationships between variables by controlling a priori for a wide range of patient and situational factors, thereby increasing the validity of estimates and inferential tests. In betweengroups analyses, variables that are related to outcome which differ between groups will be included as predictors in a logit model predicting group assignment, and the predicted values of this model will be incorporated as a covariate in all subsequent analyses. This includes factors that could influence treatment response [125-127], including number of prior episodes (>2 or not), treatment response vs. remission during treatment, and sex [128]. Continuously distributed outcomes will be summarized with the sample size, mean, standard deviation, median, minimum and maximum and categorical or binary outcomes with counts and percentages. Distributions will be examined to identify potentially influential observations (outliers) and suggest transforms (e.g., log) to normalize. The final report containing formatted tables and embedded graphics will be produced in Microsoft Word directly from the database using the SAS Output Delivery System. Analyses will use all subjects with usable data. All statistical testing will be two-sided with a significance level of 5%. The Holm-Bonferroni step down method will be applied as necessary to correct for multiple testing. SAS Version 9.2 for Windows (SAS Institute, Cary, North Carolina) will be used throughout.

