Tolerability and Safety: We will determine incidence rates for all adverse events and treatment emergent adverse events will be determined using the SAFTEE. Treatment emergent adverse events will be defined as those that were not present before the first administration of drug, but occurred after the first administration, or that were present before the first administration but increased in severity or frequency after the first administration. Incidence rates for all adverse event and treatment emergent adverse events will be compared between medication groups using chi-square for frequencies with any events or Poisson regression for counts of numbers of events adjusting for time at risk using log time as an offset variable. The numbers of subjects withdrawing from the study for each reason will also be compared across groups using survival analysis on time to study discontinuation.

Version #: 17, IRB #203076

PI: [name]

**Testing Hypothesis 1**. Both antidepressants will be efficacious based on change in Ham-D scores over time. The primary analyses will be mixed effects regression models with repeated measures (baseline, 1, 4, 8, 12 weeks) performed separately in the medication groups. The fixed effect is time, and the hypothesis test is an *a priori* contrast comparing the baseline value with the average of the four post-baseline values. In secondary analyses, patients will be categorized as responders and remitters, with response defined as a 50% or greater improvement in Ham-D score with total score ≤ 15 at the 12 weeks compared with baseline and remission [129] as having had a treatment response plus a final Ham-D score ≤7.

**Testing Hypothesis 2**. Changes in cognition, fatigue, and depression will be evaluated between and within treatment groups. Changes in BFI and cognition should be greater in bupropion SR-treated patients [30, 32, 89, 130-140]. These analyses will use mixed effects regression models with repeated measures. Treatment group, time and their interaction are the fixed independent variables. Change in Ham-D, BFI and cognitive dysfunction (3MS, MSIT, and n-back performance) are the time-varying dependent variables. All subscales of the BFI will be summarized by time point.

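### The Hypothesis 2 model leaves out the baseline covariate behind its stated power of 0.80 and does not say which term is the test

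*Combined protocol and SAP*

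**What the plan says.** The sample-size paragraph (Data Analysis, Statistical Considerations, and Testing of Hypotheses) sets up Hypothesis 1 first: "We specified a medium effect size averaged across the postbaseline measures", and "We specified compound symmetry among the measures with r=0.50". It then turns to the between-group question of Hypothesis 2: "Specifications were as above but the effect size was adjusted for the use of a baseline covariate". The layout is given as two arms of 20 patients, each measured four times. On that basis "power is 0.80 to detect a standardized mean difference (Cohen's d) of 0.6". The size of the adjusted effect is not given. General Methods sets two-sided testing at 5%.

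Under Testing Hypothesis 1 the test is explicit: an a priori "contrast comparing the baseline value with the average of the four post-baseline values". Under Testing Hypothesis 2 there is only a model. "Treatment group, time and their interaction are the fixed independent variables", and the outcomes are change in Ham-D, BFI, 3MS, MSIT and n-back performance. No baseline covariate is listed, and no coefficient, contrast or visit is named as the test.

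Table 1 schedules Ham-D and BFI at baseline and at eight later visits. It schedules MSIT, n-back and 3MS at baseline, week 4 and week 12 only.

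**The concern.** The power statement and the analysis model describe different analyses. The first credits the trial with the precision gained from a baseline covariate; the second does not include one. If the model is fitted as written, the comparison of bupropion with fluoxetine on fatigue and cognition has clearly less than the stated power.

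The missing designation adds a second problem. A model with group, time and their interaction yields at least two candidate answers: the group effect averaged over visits, and the interaction. They test different things and can disagree. If neither is fixed in advance, the choice can be made after the results are seen. These estimates are meant to support a later definitive trial, so it should be clear which quantity is being estimated.

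**Working it through.** **Inputs from the plan.** 20 per arm; d=0.6 on the scale of a single score (SD 1); r=0.50 between all pairs of measures, baseline included; four occasions, taken as post-baseline because the Hypothesis 1 specifications carry over; two-sided 5%. No dropout is modelled.

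**Assumption.** The plan does not give the covariate-adjusted effect. I take 0.6/√(1 − 0.5²) = 0.693.

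**1. Check of the setting on Hypothesis 1.** The variance of the mean of four measures is (1 + 3×0.5)/4 = 0.625. The variance of mean post-baseline minus baseline is 0.625 + 1 − 2×0.5 = 0.625. The noncentrality is 0.5/√(0.625/20) = 2.83 on 19 df, which gives power 0.765. The plan states 0.78, so the setting is right.

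**2. The stated 0.80 for Hypothesis 2.** The standard error of the averaged arm difference is √(0.625×2/20) = 0.25. The noncentrality is 0.693/0.25 = 2.77. Power is 0.791 by normal approximation and 0.771 by t on 38 df. The stated figure therefore reproduces as a baseline-adjusted arm difference averaged over visits.

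**3. The model as written, group effect on change scores.** The variance of the mean change is 0.625, as in step 1. The noncentrality is 0.6/0.25 = 2.40. Power is 0.648 by t and 0.670 by normal approximation; a simulation of 20,000 trials gave 0.65. About 28 per arm would be needed for 0.80, against 21 under step 2 (both by normal approximation).

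**4. Full analysis of covariance on the post-baseline mean.** The residual variance is 0.625 − 0.5² = 0.375. The noncentrality is 0.6/√(0.375×2/20) = 3.10. Power is 0.855 by t and 0.872 by normal approximation.

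**5. The group-by-time term.** It responds only to variation of the arm difference between visits. Its noncentrality is the sum of squared deviations of the visit-specific differences from their mean, divided by (1 − 0.5)×2/20 = 0.05.

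| Assumed arm differences | Sum of squares | λ | Power |
|---|---|---|---|
| Change scores, flat at 0.6 | 0 | 0 | 0.05 (simulation 0.051) |
| Change scores, 0.24, 0.48, 0.72, 0.96 (mean 0.6) | 2×0.36² + 2×0.12² = 0.288 | 5.76 | 0.49 on 3 df |
| Raw scores with baseline as a level, 0 then flat 0.6 | 0.48² + 4×0.12² = 0.288 | 5.76 | 0.44 on 4 df |

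For the ramp, a 1-df linear interaction gives 0.67 by normal approximation.

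**6. Cognition, two post-baseline visits.** The variance of the mean is (1 + 0.5)/2 = 0.75, and the variance of the mean change is 0.75 + 1 − 1 = 0.75. All powers are by t on 38 df.

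- Unadjusted change: 0.6/√(0.75×2/20) = 2.19, power 0.57.
- Effect inflated for the covariate: 0.693/√(0.75×2/20) = 2.53, power 0.69.
- Full analysis of covariance: residual variance 0.75 − 0.25 = 0.50, noncentrality 0.6/√(0.50×2/20) = 2.68, power 0.74.

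**The case against.** A reader might infer that the planned analysis is blind to the effect it was powered for, because the interaction on change scores has power of only 0.05. The documents do not support that.

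- The plan nowhere says that the difference is constant over visits. It speaks of a standardized mean difference, with specifications carried over from an effect averaged across visits, and an average does not fix a profile. Flexible dosing, with fluoxetine adjusted up to week 10, makes a flat difference from week 1 far from certain.
- When change is the outcome, a difference in change between the drugs is the group main effect. That term is in the model and can detect the difference. The sample-size section frames Hypothesis 2 as between-group differences, which supports the same reading. What is missing is the designation, not the term.

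A reader might also infer that 0.80 is a miscalculation. It is not: it reproduces to within a point under baseline adjustment.

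It could be said that baseline enters by another route. General Methods adds a covariate built from outcome-related variables that differ between arms, and the exploratory analyses consider baseline Ham-D. The first is conditional on imbalance and models assignment, so it is not the outcome's own baseline. The second is exploratory and does not mention baseline BFI or cognition. Neither supplies the covariate assumed in the power calculation.

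Finally, this is a pilot, and the choice of an averaged contrast over a late-visit one is partly preference. That lowers the stakes but does not remove the mismatch, since the plan states formal hypotheses, a 5% level and a power figure.

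**Conclusion.** The concern holds as a mismatch between the power statement and the model, joined to an undesignated test. As written, the averaged group difference has power of about 0.65 (0.67 by normal approximation) for d=0.6, against the stated 0.80. Baseline adjustment brings it to 0.77 to 0.79, or 0.855 with full analysis of covariance. For cognition, neither version reaches 0.80 with the visits scheduled.

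These figures rest on the plan's own r=0.50 compound symmetry, 20 analysed per arm, and my assumption about how the effect was adjusted. The interaction figures of 0.05 and 0.49 are conditional on profiles that I chose. They show only that the interaction is not a substitute for the averaged difference, not what its power will be in this trial. The omitted covariate is the firmer part of the point; without it, the undesignated test would be little more than a missing detail.

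**What to change.** In Testing Hypothesis 2:

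- Add the baseline value of each outcome as a covariate.
- Name the test as the 1-df between-arm difference averaged over the scheduled post-baseline visits, taken from the group-by-visit model, and list those visits for each outcome. Report group-by-time as secondary.

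In the sample-size section:

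- Give the adjusted effect size that was used.
- Restate the power for 3MS, MSIT and n-back on two post-baseline visits: about 0.69 to 0.74 with baseline adjustment (0.57 without).

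This takes a few sentences and no new data. It matches the test to the power calculation and parallels the Hypothesis 1 contrast. The price is that an averaged difference is less sensitive to an effect that appears only late; the secondary group-by-time result covers part of that.

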#### The Specific Aims of this study are:

Aim 1: Determine the efficacy of bupropion and fluoxetine in treatment of MDD in CKD patients.

**Aim 2**: Determine whether longitudinal change in MDD symptoms, cognitive dysfunction, and fatigue differ between bupropion and fluoxetine.

**Aim 3**: Determine whether longitudinal change in MDD symptoms, cognitive dysfunction, and fatigue correlate with change in inflammation, measures of TRP availability to brain, or neurotoxic TRP metabolites.

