# Hypotheses:

- 1) Bupropion and fluoxetine will both show efficacy in treating MDD;
- 2) Bupropion will lead to greater improvement in cognitive dysfunction and fatigue than fluoxetine; and
- 3) Change in cognition and fatigue over time will correlate with change in C-reactive protein (CRP) and quinolinic acid and change in overall depression score will correlate with measures of TRP availability.

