After consent, subjects will be interviewed by a study staff for eligibility, including a review of medical records (if available), clinical interview, physical examination, routine blood tests, and EKG, if not already available (within one month). Psychiatric diagnosis will be established after interview using the Mini International Neuropsychiatric Interview (MINI) [75], depressive symptoms will be assessed with the Hamilton Depression (HAM-D) Scale [76], and cognitive status will be assessed using the n-back and MSIT tasks [77] and the Modified Mini Mental Status (3MS) Examination [78]. Pain will be characterized with the Physical and Psychological Pain Scale [142]. Pressure pain threshold will be measured with an Algometer [143]. Thermal pain sensitivity will be characterized with Quantitative Sensory Testing (QST). Delay discounting, MSIT and n-back will be the primary measures of cognitive function and the 3MS will be used for comparison to other studies. History of prior antidepressant treatment and response will be obtained using the Antidepressant Treatment Response Questionnaire (ATRQ) [79]. Given the underrecognized role of dental and gum disease in systemic inflammation a basic noninvasive dental evaluation will be performed by [name] at UAMS Dental Hygiene Clinic. Dialysis dose, pre- and post-dialysis body weight and blood pressure, serum urea nitrogen, albumin, serum phosphate hemoglobin, calcium, parathyroid hormone, vitamin D and lipid profile will be extracted. Measures of dialysis adequacy (kt/V) will also be extracted.

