**Testing Hypothesis 3**. These analyses will measure the association between CRP, TRP availability, and quinolinic acid to Ham-D score, BFI, and cognitive measures over time. Because the effects of TRP on brain 5-HT is best estimated by the ratio of free TRP to LNAA, this ratio will be calculated and used as the primary measure of possible brain 5-HT depletion. The analyses will use mixed effects regression with time, the TRP/LNAA ratio, and their interaction as independent variables and measures of depressive symptoms (HAMD) and cognitive dysfunction (3MS, n-back accuracy, and MSIT reaction time) serving as dependent variables. Supplemental analyses will be done using the presence of residual depressive symptoms (yes: HAM-D>15; no: HAM-D<=15) and presence of cognitive impairment (yes: 3MS <80, no: 3MS ≥80), presence of dental disease (yes/ no) over time (1, 4, 8 and 12 weeks) using the generalized linear model (GEE) with the same fixed effects and binomial error.

Exploratory Analyses: Additional analyses will explore age, sex, baseline depressive symptoms (HAMD), baseline dental disease and interactions of these covariates with the fixed effects in the models described above. McNemar's test will be used to compare the proportion of subjects meeting criteria for cognitive dysfunction at baseline compared with study end, and chi-square tests to compare these proportions with population rates. Pearson correlations will be used to assess the strength of associations between variables at each assessment. Correlations between the measures of depression, cognitive function, and fatigue will be tabled and summarized with scatter plots across all time points and by time point. Exploratory analyses will also substitute individual cytokines and the ratio of pro- to anti-inflammatory cytokines for inflammation in relevant analyses and also seek to define whether there is a threshold for individual cytokines or the pro/anti-inflammatory ratio before depressive symptoms (HAM-D>8) or cognitive dysfunction occur. The threshold analysis will utilize traditional receiver-operator characteristics (ROC) analyses. Both buproprion SR and Fluoxetine are local standard practice.

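### Hypothesis 3 has no written model for CRP, quinolinic acid or any marker-fatigue link, the TRP/LNAA model does not clearly test change with change, and the GEE lists weeks without paired data

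*Combined protocol and SAP*

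**What the plan says.** The Hypotheses section states: "Change in cognition and fatigue over time will correlate with change in C-reactive protein (CRP) and quinolinic acid". It also expects change in the overall depression score to correlate with TRP availability. Aim 3 is broader and asks whether changes in depressive symptoms, "cognitive dysfunction, and fatigue correlate with change in inflammation, measures of TRP availability to brain, or neurotoxic TRP metabolites".

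Testing Hypothesis 3 opens with a matching promise: "These analyses will measure the association between CRP, TRP availability, and quinolinic acid to Ham-D score, BFI, and cognitive measures over time". The model that follows is narrower: "The analyses will use mixed effects regression with time, the TRP/LNAA ratio, and their interaction as independent variables". Its outcomes are Ham-D, 3MS, n-back accuracy and MSIT reaction time. Determination of Sample Size agrees on the marker: "The analyses for Hypothesis 3 involves using the TRP/LNAA ratio as a covariate in mixed effects regression models". It adds that design and analysis follow the between-groups models of Hypothesis 2.

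A supplemental GEE with the same fixed effects is set at weeks 1, 4, 8 and 12. Exploratory Analyses adds "Pearson correlations will be used to assess the strength of associations between variables at each assessment", and plans to "substitute individual cytokines and the ratio of pro- to anti-inflammatory cytokines for inflammation in relevant analyses".

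On cognition, the Research Plan says: "Delay discounting, MSIT and n-back will be the primary measures of cognitive function and the 3MS will be used for comparison to other studies". The Hypothesis 3 model includes 3MS and leaves delay discounting out.

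**The concern.** Three gaps meet in one short section.

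- **Coverage.** The first limb of the hypothesis (CRP and quinolinic acid with cognition and fatigue) is announced but has no model: no predictor form, tested term or visits.
- **Estimand.** The hypothesis is about change with change. A time-varying marker entered at its raw level against a raw-level outcome picks up any tendency for patients with higher markers to be more impaired throughout. The time-by-marker interaction asks whether the slope differs between visits, which is another question.
- **Visits.** Some GEE weeks have no marker or no outcome.

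Left as it is, the choice of marker, outcome, visits and tested term falls to the analyst after the data are in. A stable difference between patients could then be reported as correlated change.

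**Working it through.** **1. Coverage.** The Hypotheses section implies five marker-domain pairs: CRP with cognition and with fatigue, quinolinic acid with cognition and with fatigue, and TRP with depression. One of the five is modelled (TRP-depression). The opening sentence of Testing Hypothesis 3 implies 3 markers x 3 domains = 9 pairs. Two of the nine are modelled (TRP-depression and TRP-cognition). BFI is modelled under Hypothesis 2, but only by treatment and time. The Pearson correlations are taken within each assessment, so they are cross-sectional. The cytokine substitution refers to an inflammation model that is not written.

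**2. The plan's own power figure.** Inputs from Determination of Sample Size are n = 20 per group, four occasions, correlation 0.50, d = 0.6 adjusted for baseline, and two-sided alpha 0.05.

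- Variance of the mean of four occasions: (1 + 3 x 0.5)/4 = 0.625
- Adjusted effect: 0.6/sqrt(1 - 0.25) = 0.693
- Standard error: sqrt(2 x 0.625/20) = 0.25
- Power: Phi(0.693/0.25 - 1.96) = Phi(0.81) = 0.79, against 0.80 stated
- Conversion: r = 0.6/sqrt(0.36 + 4) = 0.287, consistent with the stated value of roughly 0.30

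The arithmetic for Hypothesis 2 stands. Hypothesis 3 then borrows this four-occasion design.

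**3. What the coefficient measures.** Write the marker as m_it = M_i + (m_it - M_i), the person mean plus the within-person deviation. In y_it = time_t + b m_it + u_i + e_it, b is a weighted mix of the slope on M_i and the slope on the deviation. Only the second is change with change.

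Simulation: 40 patients, random intercept, time as a factor, three visits, true within-patient link zero. The ICCs and between-patient correlations are assumptions; the documents give none.

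| Between-patient r | Raw marker, ICC 0.5-0.7 | Raw marker, marker ICC 0.3-0.7 and outcome ICC 0.5 |
|---|---|---|
| 0.3 | 13-18% | 11-21% |
| 0.5 | 30-43% | 20-50% |
| 0.7 | 57-76% | 29-84% |

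The within-person deviation rejects in about 4-7%. The raw coefficient can also hide a real link. With within-patient r = 0.3 and between-patient r = -0.5 (ICCs 0.5), its power is 29% at three visits, against 78% for the deviation.

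With change-from-baseline outcomes, the raw marker coefficient rejects in about 4-7%.

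**4. Visits.** Table 1 has blood at B, 1, 4 and 12; 3MS, n-back and MSIT at B, 4 and 12; Ham-D and BFI at every visit. Against the GEE weeks 1, 4, 8 and 12:

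- Ham-D with marker: 1, 4, 12 (3 of 4)
- 3MS with marker: 4, 12 (2 of 4)

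Biochemical Measurements lists marker draws at weeks 1, 4 and 12 only. Table 1 marks blood at B without saying what is assayed.

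**5. Power on paired visits.** For the within-person term, residual df = 39(k - 1) - 1, which gives 38, 77 and 116 for k = 2, 3 and 4 visits. By Fisher z, power at r = 0.3 is Phi(0.3095 x sqrt(df - 1) - 1.96), or 47%, 77% and 91%. Simulation gives 46-49%, 74-79% and about 91%. These figures assume no dropout and come before any multiplicity correction or arm terms.

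**6. Treatment arm.** Purpose and Objectives expects bupropion to lower cytokines, cognitive impairment and fatigue more than fluoxetine. A within-person term with a common time effect absorbs such a shared shift. With no link inside either arm and assumed shifts in both variables, it rejects in about 7% (0.6 SD) and 16-34% (1.0 SD). Adding arm-by-time restores 3-5%.

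**The case against.** The strongest reply is that the text is under-specified, not silent. The opening sentence of Testing Hypothesis 3 does commit to CRP, quinolinic acid and BFI over time. The sample-size section refers to the Hypothesis 2 plan, whose dependent variables are changes in Ham-D, BFI and cognition. Read that way, fatigue and change outcomes carry over and the inflation in step 3 goes. This stands as an open reading, but the Hypothesis 3 model sentence does not repeat it and lists other outcomes. Even on that reading the marker is not stated as a change.

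A reader might infer that the plan gives no longitudinal result for fatigue. It does, under Hypothesis 2; what is missing is the link from any marker to fatigue.

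It is also fair that this is a pilot, the GEE is supplemental, and General Methods analyses all subjects with usable data. That limits the seriousness of the week mismatch, but an outcome or marker not scheduled at a visit cannot be used there.

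**Conclusion.** The concern holds in this form. Two of the three named markers, and every marker-fatigue pair, lack a written model. The TRP/LNAA model does not say which term is tested or whether outcomes are levels or changes. The GEE weeks do not match the schedule.

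The false-positive rates in step 3 apply only to raw-level outcomes and rest on assumed ICCs and correlations, so it would be wrong to say outright that the planned test is inflated. That a raw-on-raw coefficient mixes the two associations does not depend on those values. Nor is the stated power of 0.80 miscalculated; it belongs to a four-occasion comparison of groups. The schedule gives Hypothesis 3 two to four paired visits, depending on the outcome and on whether markers are assayed at baseline. No size can be fixed for the multiplicity penalty, because General Methods applies Holm only where needed and defines no family.

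This should be fixed before analysis. It does not undermine the main efficacy question.

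**What to change.** In Testing Hypothesis 3:

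1. **Models.** Write models with CRP and with quinolinic acid as predictors of BFI and of each cognitive measure. Keep TRP/LNAA with Ham-D as the other hypothesised test and label all remaining pairs secondary. Reconcile this section with the Research Plan on delay discounting versus 3MS.
2. **Tested term.** State whether outcomes are levels or changes. Split each marker into person mean and within-person deviation, or use change scores on both sides, and name the within-person or change term as the test. Include arm and arm-by-time. The version without arm-by-time may be reported as a secondary total association.
3. **Visits.** Reconcile Biochemical Measurements with Table 1 on the baseline assay, then use only visits with both marker and outcome. If baseline is assayed: B, 4, 12 for 3MS, n-back and MSIT, and B, 1, 4, 12 for Ham-D and BFI. If not: 4, 12 and 1, 4, 12. Use 1, 4, 12 for the GEE on Ham-D above 15, because entry requires a score above 17 and nearly everyone would be positive at baseline.
4. **Multiplicity and power.** Define the Hypothesis 3 family and restate the detectable effect for the visits available.

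Cost: eight more hypothesised models (2 markers x BFI and three cognitive measures), or ten if both delay discounting and 3MS are kept, with no new visits. The within-person term is less efficient than the pooled coefficient, arm-by-time takes a few degrees of freedom, and more tests mean a stricter correction. If the family were nine tests (an assumption), Fisher-z power at r = 0.3 at the first Holm step would be about 19%, 47% and 71% with two, three and four visits. For a pilot, intervals should be reported beside the tests. Dental-assessment timing and optional covariates are separate minor points.

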# **4. Study population** is defined as CKD patients with chronic kidney disease with MDD. **Inclusion Criteria**

- age 30-70 vrs:
- meet the Diagnostic and Statistical Manual of Mental Disorders, 4th Edition (DSM-IV) criteria for MDD;
- have a Ham-D score > 17
- if receiving any of these medications, on a stable or maintenance dose of iron or erythropoietinstimulating agents, statins, angiotension receptor blockers and/or angiotension converting enzyme inhibitors, phosphate binders and vitamin D receptor analogs as these agents may influence cytokines proposed in the study;
- serum albumin of ≥ 3.2 g/dl, serum phosphate of <6.5 mg/dl, and serum hemoglobin of ≥9 mg/dl in two consecutive blood tests [subjects failing screening due to these blood tests will be allowed to be re-screened in 30 days];

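### In the Hypothesis 1 Ham-D models, the exploratory interaction of baseline Ham-D with time is confounded with regression to the mean and cannot show that sicker patients benefit more

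*Combined protocol and SAP*

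**What the plan says.** All of this stands under the heading Data Analysis, Statistical Considerations, and Testing of Hypotheses, except the entry criterion.

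- **Testing Hypothesis 1** specifies "mixed effects regression models with repeated measures (baseline, 1, 4, 8, 12 weeks) performed separately in the medication groups. The fixed effect is time". The hypothesis test contrasts baseline with the average of the four later values.
- **Testing Hypothesis 2** uses treatment group, time and their interaction as fixed effects, and states that "Change in Ham-D, BFI and cognitive dysfunction (3MS, MSIT, and n-back performance) are the time-varying dependent variables". It does not list the visits that enter the model.
- **Exploratory Analyses** adds covariates to those models: "Additional analyses will explore age, sex, baseline depressive symptoms (HAMD), baseline dental disease and interactions of these covariates with the fixed effects". Which interaction goes with which outcome is not specified.
- **Determination of Sample Size** gives the correlation used for planning: "We specified compound symmetry among the measures with r=0.50 because the measurements are relatively close in time". It also mentions a structure falling from .50 to .32, without the values in between.
- **Inclusion Criteria** (section 4) select on the same scale: "have a Ham-D score > 17".

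Nothing in the plan mentions regression to the mean, and there is no untreated arm that would reveal it.

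**The concern.** Time is the only fixed effect in the Hypothesis 1 models, so the only interaction that the exploratory sentence can create there is baseline Ham-D by time. On the baseline row the outcome is the covariate, and its slope is exactly 1. On later rows the slope is whatever the visit-to-visit correlation and the SDs make it, usually less than 1. The interaction measures that drop. It would be present if the drug did nothing, and equally if the drug shifted every patient by the same amount.

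The result would read as greater improvement in more severely depressed patients. A primary goal of the pilot is to support the design of a definitive trial, and severity at entry is a natural design question for it. An exploratory label warns the reader about chance findings. It does not warn about a bias with a predictable direction. Age, sex and baseline dental disease do not share the problem, because none of them is a component of the outcome.

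**Working it through.** **Inputs from the plan.** 20 patients per arm, 40 in all; r = 0.50 with compound symmetry; four post-baseline visits; d = 0.5 for Hypothesis 1; two-sided 5% tests. **Assumed, because the plan does not give them:** the Ham-D SDs at baseline and later, and where the entry cut falls in the baseline distribution.

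**1. The plan's own figure.** In SD units, the variance of the mean of four post-baseline values is (1 + 3 × 0.50)/4 = 0.625. The SD of (post mean − baseline) is √(0.625 + 1 − 2 × 0.50) = 0.791. The noncentrality is 0.5/0.791 × √20 = 2.83, and the paired t-test power is 0.765, against 0.78 stated. With mixed-model degrees of freedom (76) it is 0.797, against the plan's simulated 0.79. The set-up is therefore the plan's.

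**2. Expected slope with no drug effect.** Regress (post mean − baseline) on baseline:

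slope = r × (post SD / baseline SD) − 1.

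At r = 0.50 with equal SDs this is 0.50 − 1 = −0.50. The correlation of baseline with change is −0.50/0.791 = −0.632. At r = 0.70 the slope is −0.30 and the SD of change is √(0.775 + 1 − 1.40) = 0.612, so the correlation is −0.490.

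**3. False-positive rate in one arm (n = 20).** Simulated with no mean change and complete data; the test is baseline Ham-D by the plan's own contrast (1 df).

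| Assumption | Slope | Rejection at nominal 5% |
|---|---|---|
| r = 0.50, equal SDs | −0.50 | 0.88–0.89 |
| r = 0.70, equal SDs | −0.30 | 0.62 |
| r = 0.80, equal SDs | −0.20 | 0.43 |
| r = 0.50 before selection, baseline cut at its mean | −0.50 | 0.50 |
| r = 0.70 before selection, baseline cut at its mean | −0.30 | 0.28–0.29 |
| r = 0.50, post/baseline SD ratio 1.25 | −0.37 | 0.51 |
| r = 0.50, ratio 1.5 | −0.25 | 0.20 |
| r = 0.50, ratio 2.0 | 0 | 0.05 |

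At r = 0.50 with equal SDs, every significant result ran in the direction of sicker patients improving more. Selecting on baseline leaves the slope unchanged but narrows the covariate, which lowers the rate. If the interaction is tested over all five visits (4 df), the rate is about 0.62, or 0.23 with baseline cut at its mean. An unrelated covariate by time rejects in 0.045 of trials.

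**4. Hypothesis 2 (n = 40, r = 0.50, equal SDs).** The outcome is change in Ham-D, with baseline inside it.

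- Main effect of baseline Ham-D on change: significant in more than 0.99 of trials, or 0.83 with baseline cut at its mean.
- Baseline Ham-D by time over post-baseline visits: 0.050 under compound symmetry. It is 0.136 if the correlations are assumed to fall linearly from .50 to .32.
- Baseline Ham-D by treatment group: 0.048, with change or with the post-baseline mean as outcome.

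If the Hypothesis 2 model kept a baseline row, the coupling would move into baseline by time, as in Hypothesis 1.

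**The case against.** Much of the opposing case stands. The slope is not a fixed −0.5: it depends on the SD ratio, and the plan gives no SDs. The entry cut restricts baseline only, which pushes that ratio up. The plan names no contrast for the exploratory interactions, so the 4-df test with its lower rate is at least as likely. The planned outputs of the pilot are largely feasibility, tolerability and disposition, and no sentence says that this interaction will set an entry threshold or be read as effect modification. Interactions with the fixed effects already include baseline by treatment group, which is valid.

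A reader might go further and infer that the severity result will come out significant in each arm and overall, whatever the drug does. The documents do not support that:

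- The arms are fitted separately, so significance in both needs the product of the two rates: 0.89² = 0.79 at best, and 0.50² = 0.25 with baseline cut at its mean.
- Hypothesis 1 has no pooled model. The figure above 0.99 at n = 40 is a main effect of baseline on change in the Hypothesis 2 setting, not the interaction with time.
- A drug effect that truly varied with severity would move the slope too. The term mixes the two sources; it is not pure artefact.

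Nor can one infer that the comparison of the two drugs is compromised, since baseline by treatment group keeps its size.

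One defence fails. The plan says "The Holm-Bonferroni step down method will be applied as necessary to correct for multiple testing", but a multiplicity correction does not help: the association is really in the data, and only its interpretation is wrong.

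**Conclusion.** The point holds for Ham-D outcomes. In the Hypothesis 1 models the planned interaction cannot separate regression to the mean and mathematical coupling from effect modification. With the plan's correlation, equal SDs and no drug effect, it misleads in about 0.89 of trials per arm on the 1-df contrast. Across the assumptions examined, that rate runs from 0.89 down to nominal, and reaches nominal only when the post-baseline SD is twice the baseline SD. In Hypothesis 2 the same coupling sits mainly in the main effect of baseline Ham-D on change in Ham-D.

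The primary contrast, the randomised comparison, and the models for BFI, 3MS, MSIT and n-back are untouched. Because the analysis is exploratory, this is a point to consider rather than a defect in the trial's main conclusions.

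**What to change.** In the Exploratory Analyses paragraph:

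1. Exclude baseline Ham-D by time from any Ham-D model that keeps baseline Ham-D as an outcome row.
2. Assess severity as an effect modifier only through baseline Ham-D by treatment group, in the between-drug model of post-baseline Ham-D (or change in Ham-D), with baseline Ham-D as a main effect. The two outcomes give the same interaction test.
3. State that neither within-arm slopes of change on baseline nor the pooled main effect of baseline Ham-D on change in Ham-D will be interpreted as effect modification.

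Age, sex and dental disease can stay as planned, and baseline Ham-D can remain a moderator for the non-Ham-D outcomes.

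The cost is a few sentences and no new data. A within-arm severity result is no longer offered as evidence, and the randomised interaction test that replaces it has low power with 20 patients per arm. A non-significant result there should not be read as showing that severity is irrelevant.
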